## 11.6 Data Analysis Plan: Complete description: Background, Objectives, Design, Step by Step how the project is going to be done, Data analysis plan:

Outcome analyses are exploratory as this is a pilot study. We will conduct these analyses to assess for a potential early efficacy signal as well as to inform future meta-analyses that aggregate our findings along with others to glean more definitive insights into the potential efficacy of NAC for an array of conditions.

Baseline values of continuous outcome variables will be tested for normality using the Shapiro-Wilk test (Razali & Wah, 2011). If normally distributed ( $< \pm 2$  skew and excess kurtosis), linear mixed-effects models (LMMs) will be used to evaluate the changes between baseline to post-treatment across the study groups taking into account within-subject associations over time. This approach is ideal for intention-to-treat analyses, because it uses all available data, and therefore all participants, including those with missing data, with no required imputations (Gueorguieva & Krystal, 2004). Furthermore, this approach reduces the variability of estimates by using all of the observations of the primary outcome measure, not just the baseline and treatment completion data points. In the event the data are not normally distributed, generalized linear mixed-effect models (GLMMs) will be applied to accommodate non-normal distributions in the data (Lo & Andrews, 2015). Fixed effects in the model will include the baseline outcome measure, treatment assignment, and a categorical time point. We will obtain adjusted, absolute between-group changes in outcome at each time point by including an interaction term between time point and treatment assignment (Espie et al., 2019). The model will also include a random participant-level effect. Sensitivity analyses will be conducted. Consistent with recommendations (e.g., Hallgren et al., 2016), items measured daily (i.e., drinks per drinking day, percent drinking days, percent days marijuana smoking, and cigarettes per day), will be aggregated into ~two-week averages corresponding to time between each session prior to statistical analysis.

Given the exploratory nature of the analyses, we will report both false discovery rate corrected (separated by primary, secondary, and tertiary aims) and nominally significant findings. We will run the primary analyses using all participants, and then re-run the analyses only using participants who had at least one follow-up session (i.e., "available cases"; Abraha et al. (2015)) and adherence of >80% as verified by the pill count and self-report (e.g., Gray et al. (2017)).

We will also assess marijuana and cigarette use if we have ample cases ( $N \geq 10$  in each group). Percent days marijuana smoking and cigarettes per day from baseline to the final session will also be assessed using LMMs (or GLMMs), but will be restricted to the subsets of individuals who report using marijuana and cigarettes, respectively, in the past month at the baseline session. For categorical smoking outcomes, chi square tests will assess for differences in rates of point prevalence abstinence (7 days at the end) and floating abstinence (any 7 day stretch). Missing cases will be assumed as having no abstinence on those days.

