### **10.0**

#### **Study Procedures, Data Management, and Privacy**

##### **10.1 Study Procedures:**

Describe step-by-step how the study will be conducted from beginning to end

Individuals will be recruited from the Addiction Treatment Services center at WRNMMC. Specifically, the study team will post flyers on tables around ATS and will provide ATS staff with study flyers and a description of the research study. Preexisting patients as well as new patients will be informed of the study by ATS staff and provided a flyer. The ATS staff have agreed to mention the study both in individual and group settings (IOP). Study staff may also come to discuss the research study as requested by ATS. The study will typically be discussed with patients on the day of their intake. They will inform patients that it is a 7-week clinical trial of an experimental medication for AUD taking place at USU on base. It will not interrupt their current treatment and thus they can participate while in treatment at ATS. Given the exclusion criteria, focus will be on patients who have not opted to take an FDA approved medication for AUD. The ATS providers will wait to verbally inform patients about the study until after they have had an opportunity to be evaluated and recommended for FDA approved medication for AUD (e.g., naltrexone). Only those that are not taking FDA approved medications will be enrolled in the study. If they change their mind after enrolling in the study and want to take an FDA approved medication we will encourage them to discuss with their provider and follow their clinical recommendations. This will not impact their participation in the study and we will control for it statistically in our analysis.

Interested individuals will contact the research team and be screened over the phone for eligibility, then eligible participants will be scheduled for their baseline visit, ideally 1-3 weeks after the phone screen. Phone screening procedures are outlined in the table in 10.2. All in-person visits will take place at buildings 17 and 53 of the Uniformed Services University. 1-2 days prior to each scheduled appointment, participants will be called to confirm the appointment and screened for COVID symptoms. If any COVID symptoms are endorsed, they will be rescheduled and told to get tested for COVID and see their primary care provider (see NAC COVID screen and COVID screen phone call docs for additional details).

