Participants with a BAC of 0 will complete the informed consent process. They will undergo a physical exam by the physician. During the physical, female participants will undergo a pregnancy screen using a pregnancy test kit. If the screen is positive, they will be told they are not eligible to participate and they will not be counted in the study's enrollment number. Further, they will be instructed to contact their primary care provider to confirm the results and discuss the risks of alcohol use during pregnancy. Next, the RA will conduct the MADRS interview, then participants will complete the TLFB self-report form. They will then complete the computer questionnaires (demographics, ASSIST, AUDIT, APT, PACS, DDT, SIAS-6, SPS-6, e-cigarette questions, HONC, GAD-7, mental health services, medications and supplements, and military service questions) and behavioral tasks (Stop Signal, N-back, and Trail Making). Participants will be asked the treatment questions and referred to mental health resources by the RA. They will then be scheduled for their next study session and complete payment paperwork with the RA. Then they will be randomized to either 7 weeks of oral NAC (3000 milligrams) or 7 weeks of placebo. We will advise participants to inform their provider of participating in this research study and of taking 3000mg NAC or placebo. Participants will be given a business card to give to their provider stating they are in the study and taking 3000mg of NAC or placebo. Participants will be instructed to go to the Investigational Pharmacy (building 9) immediately after their appointment to pick up their study medication. They will be escorted by the RA if they have never been before or don't remember how to get there. The pharmacy will handle gender stratified randomization. The first study session will take approximately 3 hrs to complete.

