### Self-report:

1. **Demographics:** We will ask age, sex, years of education, ethnicity/race, weight, height, marital status, college student status, employment status, and pretax household income. Duration: 2 minutes.
2. **Alcohol, Smoking, and Substance Involvement Screening Test (ASSIST).** A measure of current, recent, and lifetime drug use, which has been modified to remove redundant questions regarding alcohol and smoking. Duration 3 minutes. (Humeniuk, Henry-Edwards, Ali, Poznyak, & Monteiro, 2010).
3. **Alcohol Use Disorder Identification Test (AUDIT).** A 10-item measure of alcohol use and misuse. Duration: 2 minutes. (Saunders, Aasland, Babor, De La Fuente, & Grant, 1993)
4. **Alcohol Purchase Task (APT).** 17 item measure assessing preferences for alcohol at various prices. Duration 3 minutes. (Kaplan et al., 2018)
5. **Penn Alcohol Craving Scale (PACS):** The PACS is a 5-item measure of craving for alcohol over the past week. Each item is rated on a scale from 0 to 6. This self-report form takes approximately 3 minutes to complete. (Flannery, Volpicelli, & Pettinati, 1999)
6. **Delayed Discounting Task (DDT).** This task assesses capacity to delay gratification. Duration: 3 minutes. (Kirby et al., 1999)
7. **Social Interaction Anxiety Scale (SIAS-6) and Social Phobia Scale (SPS-6):** 12-item measure on social anxiety and social phobia. Duration: 3 minutes. (Peters, Sunderland, Andrews, Rapee, & Mattick, 2012)
8. **TLFB alcohol/cigarette/marijuana use.** Asks clients to retrospectively estimate their daily alcohol, cigarette, and marijuana consumption over a time period ranging from 7-30 days (on the first meeting) via a self-report form. Duration: 5 minutes. (Sobell & Sobell, 1996)
9. **E-cigarette questions:** "Have you ever used an electronic nicotine product, even one or two times? Do you now use electronic nicotine products?" Duration: 1 minute. (not specifically based on any preexisting measure).
10. **Hooked On Nicotine Checklist (HONC).** A measure of nicotine use and misuse. Duration: 2 minutes. (Difranza et al., 2002)
11. **Anxiety symptoms:** Generalized Anxiety Disorder Screener (GAD-7). The GAD-7 is a 7-item self-report measure assessing symptoms of generalized anxiety disorder. Respondents use a scale from 0 ('not at all') to 3 ('nearly every day') for each symptom. Duration: 1 minute. (Spitzer, Kroenke, Williams, & Löwe, 2006)

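### Randomisation is stratified by gender but gender is not a listed term in the 11.6 model; reported SEs run slightly wide if gender is prognostic and arms are balanced within gender

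*Combined protocol and SAP*

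**What the plan says.** - **Randomisation.** Section 10.1 (Baseline Visit) states: "The pharmacy will handle gender stratified randomization". The same sentence appears in the drug details of section 18.2. Neither place describes blocking or any other restriction on allocation within gender.
- **Outcome model.** Section 11.6 states: "Fixed effects in the model will include the baseline outcome measure, treatment assignment, and a categorical time point". It adds treatment effects at each visit by "including an interaction term between time point and treatment assignment", and then: "The model will also include a random participant-level effect". For outcomes that fail the normality rule, "generalized linear mixed-effect models (GLMMs) will be applied to accommodate non-normal distributions in the data".
- **Other covariates.** Section 10.1 promises adjustment for one more variable, an approved alcohol use disorder medication started after enrolment: "This will not impact their participation in the study and we will control for it statistically in our analysis". Sections 11.1 and 11.6 do not name gender as a covariate. Sensitivity analyses are promised in 11.6 without any content.
- **What is recorded.** The demographics form in section 10.2 records sex ("We will ask age, sex, years of education"), whereas the stratification is described in terms of gender.

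**The concern.** Stratifying on a prognostic factor and balancing the arms within it reduces the true sampling variance of the treatment estimate. A model without that factor leaves its variation in the participant effect and the residual, so the model-based SE describes a less precise design than the one that was run. In a linear mixed model this does not bias the estimate. It makes intervals too wide and tests slightly conservative.

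Section 11.6 uses these analyses to look for an early efficacy signal and to supply later meta-analyses. Under inverse-variance weighting with negligible between-study variance, weight is proportional to 1/SE², so an SE that is too wide costs the trial weight. If gender has no association with outcome beyond baseline, nothing is lost.

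**Working it through.** **Inputs from the documents.** 25 per arm (section 11.4). 40 evaluable plus 10 for dropout gives 50, a 20% allowance, since 40/(1 − 0.20) = 50 (section 11.5). That figure reproduces, and it does not depend on the model terms.

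**Inputs assumed.** The documents do not give the share of women, p, or the part of the residual variance after baseline adjustment that gender explains, R². The ranges used are p = 0.20 to 0.40 and R² = 0 to 0.10.

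**Formulas** (linear mixed model, arms balanced within gender).

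1. SE reported without gender ÷ correct SE = 1/√(1 − R²).
2. Actual two-sided type I error at nominal 5% ≈ 2[1 − Φ(1.96/√(1 − R²))].
3. Gender gap g, in within-gender SDs, that produces R²: p(1 − p)g² = R²/(1 − R²).
4. Meta-analytic weight lost = 1 − (SE ratio)⁻² = R².

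Worked case, R² = 0.05:
- SE ratio: 1/√0.95 = 1.026.
- Type I error: 1.96 × 1.026 = 2.011, which gives 4.4% to 4.5%.
- Gender gap: R²/(1 − R²) = 0.0526. With p = 0.20, g = √(0.0526/0.16) = 0.57. With p = 0.40, g = √(0.0526/0.24) = 0.47.

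| R² | SE too wide by | Type I error | Gap needed (40% to 20% women) | Weight lost |
|---|---|---|---|---|
| 0 | 0% | 5.0% | 0 | 0% |
| 0.02 | 1.0% | 4.8% | 0.29–0.36 SD | 2% |
| 0.05 | 2.6% | 4.4–4.5% | 0.47–0.57 SD | 5% |
| 0.10 | 5.4% | 3.9% | 0.68–0.83 SD | 10% |

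**Simulation check.** Random-intercept model with the terms of section 11.6; weeks 1, 3, 5 and 7; week-7 contrast; complete data; participant-level share of residual variance 0.6 (assumed); 20 or 25 per arm; 20% or 40% women; 12,000 replicates per scenario.

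- SE without gender ÷ SE with gender: 1.000, 1.010–1.011, 1.027–1.028 and 1.056–1.057 at the four R² values.
- Type I error without gender: 0.048–0.053, 0.047–0.053, 0.043–0.047 and 0.036–0.039.
- True SD of the estimate, without v with gender (25 per arm, 20% women): 0.2757 v 0.2756 at R² = 0.05, and 0.2683 v 0.2679 at R² = 0.10. The precision is there either way; only the reported SE misses it.

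A separate simulation with an ordinary linear model (25 per arm, 10% to 50% women, 20,000 replicates per cell) gave SE ratios of 1.003–1.012 at g = 0.3, 1.010–1.032 at g = 0.5 and 1.024–1.080 at g = 0.8. It agrees on direction and size.

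**If allocation is not balanced within gender** (25 per arm, 30% women): type I error without gender was 0.048, 0.052 and 0.053 at R² = 0, 0.05 and 0.10, so the SE is then not conservative. Leaving gender out still gave an SE 1.9% (R² = 0.05) or 4.8% (R² = 0.10) wider than including it.

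**The case against.** The case for leaving this alone has several parts.

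- **Balance is not documented.** The conservative SE requires balance within gender, and no restriction within strata is described. This stands as a condition on the claim. Without balance the SE is valid, but a prognostic gender term would still narrow it.
- **The list may not be closed.** The wording does not exclude further terms, and the medication covariate promised in section 10.1 is also missing from 11.6. So the plan may be silent on gender rather than have decided against it. Silence still leaves the choice to be made after the data are seen.
- **The effect is assumed and probably small.** Each outcome's own baseline is already in the model and absorbs stable gender differences. The 5.4% figure needs a remaining gap of 0.68 to 0.83 SD, and nothing in the documents suggests one that large. This is fair.
- **Dropout loosens the balance.** In a simple two-arm comparison (28% women, 25 per arm, 20% lost at random), reported SE over true SD fell from 1.028 to 1.023 at R² = 0.05 and from 1.054 to 1.046 at R² = 0.10. The excess shrinks by 5/28 = 18% and 8/54 = 15%; the direction is unchanged.
- **Some outcomes may go to GLMMs.** The figures do not carry over to models with a non-identity link, where adding gender can also change the conditional treatment effect.
- **Little depends on it.** The outcome analyses are exploratory, and the plan does not say that later meta-analyses would use these SEs.

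These points keep the matter minor. They do not remove the mismatch or give a reason against a correction that costs almost nothing.

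**Conclusion.** The concern holds, as a minor point. Gender governs the randomisation and is not a listed term in the outcome model. On the linear mixed model route, with balance within gender, the reported SE is too wide by 0% to 5.4% for R² from 0 to 0.10, and by 1.0% to 2.6% for R² of 0.02 to 0.05; expected dropout makes these somewhat smaller. The error is conservative and the estimate is unbiased. The size rests on an assumed gender mix and gender effect. The sample size and the feasibility, dropout and SD aims are unaffected.

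**What to change.** In section 11.6, list the fixed effects as: baseline outcome, gender (the stratification factor, as used by the pharmacy), treatment, categorical time, and treatment-by-time. Take the value from the pharmacy's stratum variable, since the demographics form records sex. State how allocation is restricted within each gender stratum, in a place that does not compromise the blind.

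For the small subsets ("We will also assess marijuana and cigarette use if we have ample cases") and the re-run restricted to adherent participants, include gender only where the numbers of each gender in both arms allow it, and fix that rule in advance. Report the outcome SDs as planned; use a gender-adjusted SD to size the main trial only if that trial will also adjust for gender.

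The cost is one degree of freedom with two strata, or two if the pharmacy uses three. If gender is not prognostic, the simulated week-7 SE is 0.2840 without and 0.2841 with gender under balanced allocation. Without balance it is 0.2840 v 0.2862, or 0.2862/0.2840 − 1 = 0.8% wider. The sample size does not change.

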## 12.0 Participant Information

### 12.1 Subject Population:

Adult Military Healthcare Beneficiaries currently or formerly enrolled in an outpatient AUD treatment program at a MTF.

### 12.2 Age Range:

Check all the boxes that apply. If the age range of potential subjects (specimens, records) does not match the range(s) selected, please specify in the text box.

- 0-17
- 18-24
- 25-34
- 35-44
- 45-54
- 55-64
- 65-74
- 75+

18 - 74

### 12.3 Gender:

- Male
- Female
- Other

### 12.4 Special categories, check all that apply

- Minors /Children
- Students
- Employees - Civilian
- Employees - Contractor
- Resident/trainee
- Cadets /Midshipmen
- Active Duty Military Personnel
- Wounded Warriors
- Economically Disadvantaged Persons

- Educationally Disadvantaged Persons
- Physically Challenged (Physical challenges include visual and/or auditory impairment)
- Persons with Impaired Decisional Capacity
- Prisoners
- Pregnant Women, Fetuses, and Neonates
- Non-English Speakers
- International Research involving Foreign Nationals - Headquarters Review is necessary

You must also consider the requirements of DoDI 3216.02, Enclosure 3, paragraph 7.e.

Depending on your intended subjects' status, you may also need to consider the requirements of DoDI 3216.02, Enclosure 3, paragraph 7.e.

#### 12.5 Inclusion Criteria:

Order Number	Criteria
1	≥ 18 years of age.
2	Meets DSM-V criteria for alcohol use disorder on the SCID-5
3	MHS Healthcare Beneficiary NOTE: While we are recruiting explicitly from the ATS patient population, we do not require that they are currently receiving treatment at ATS. For participants that are not currently in care we will provide them with resources to pursue psychotherapy while engaged in our study as outlined in the interview treatment questions and physical and mental health resource document.

#### 12.6 Exclusion Criteria:

Order Number	Criteria
1	Lifetime clinical diagnosis of schizophrenia or bipolar disorder
2	Currently receiving medication for the treatment of alcohol use disorder including oral or injectable naltrexone (ReVia, Vivitrol), disulfiram (Antabuse), and acamprosate (Campral).
3	Pregnancy
4	Lack of English fluency sufficient to complete study measures.
5	Trying to get pregnant in the next 4 months.
6	Hospitalized because of alcohol use in the past 12 months.
7	History of seizures or delirium tremens.
8	History of liver disease
9	Diagnosis of a neurocognitive disorder (e.g., dementia, alzheimer's, intellectual disability).
10	Individuals who were never enrolled into ATS.

## 13.0

### Recruitment and Consent

#### 13.1 Please describe the recruitment process, including how subjects will be identified and selected for the study.

We will recruit for the study from the WRNMMC Addiction Treatment Services (ATS) clinic. During initial phone conversation, participants will complete a brief phone screen detailed in section 13.3.

#### 13.2 Compensation for Participation:

Non-active duty/non-federal employee participants will be paid \$265 total as follows:  
\$60 for baseline visit (1)  
\$40 per in-person visit (4)  
\$15 per phone call (3)

Participants who are active duty or federal employees are not eligible for payment. Participants will be informed on the consent form that their payment is taxable and that there is a chance that their payment could be withheld under certain circumstances. If they owe money to the government, their payment for study participation may be applied to that debt and not sent to them.

#### 13.3 Please describe the pre-screening process. If no pre-screening, enter Not Applicable in the text editor

Participants will complete a brief phone screen in which they will be asked the following eligibility criteria questions:

1. *Have you used any drugs other than marijuana in the past 30 days?*  
*If yes: Which drugs?*
2. *Have you ever had a seizure?*
3. *Have you ever had delirium tremens or DT?*
4. *Have you been to the hospital because of alcohol use in the past 12 months?*
5. *Have you ever been diagnosed with schizophrenia?*
6. *Have you ever been diagnosed with bipolar disorder?*
7. *Have you ever been diagnosed with a neurocognitive disorder such as dementia or Alzheimer's?*
8. *Have you ever been diagnosed with an intellectual disability such as mental retardation? (NOTE: ADHD is ok)*
9. *Do you have any chronic medical conditions associated with alcohol use (such as liver disease)?*
10. *Are you currently receiving medication for the treatment of alcohol use disorder? If so, what medication are you taking? [Exclude if taking oral or injectable naltrexone (ReVia, Vivitrol), disulfiram (Antabuse), and acamprosate (Campral)]*
11. *Female only: Are you pregnant or trying to get pregnant sometime in the next 4 months?*
12. *How old are you?*

SCID-5 AUD module

If they meet eligibility criteria, they will be scheduled for their baseline visit. They will be told that they need to be abstinent from alcohol for at least 24 hours before their baseline appointment and that they will be breathalyzed to confirm a BAC of 0.

#### 13.4 Consent Process: Revised Common Rule, Section 219.116: General requirements for informed consent, whether written or oral, are set forth in this paragraph and apply to consent obtained in accordance with the requirements set forth in paragraphs (b) through (d) of this section. Broad consent may be obtained in lieu of informed consent obtained in accordance with paragraphs (b) and (c) of this section only with respect to the storage, maintenance, and secondary research uses of identifiable private information and identifiable biospecimens.

Are you requesting a waiver or alteration of informed consent?

Yes  No

Please explain the consent process:

Participants will complete the consent process at the baseline visit in a private room at USU Building 53. Participants will be instructed to read the consent form and ask any questions before signing, then sign. A copy of the consent form with participant and research team signatures will be provided to participant following the consent process.

**13.5 DoDI 3216.02 requires an ombudsman to be present during recruitment briefings when research involves greater than minimal risk and recruitment of Service members occurs in a group setting. If applicable, you may nominate an individual to serve as the ombudsman.**

N/A  
 Propose ombudsman

